1.1 Background

Globally, around 140 million infants are born every year, representing 4 births/second every day. Of these, approximately 10 million infants do not breathe immediately after birth, and 60% require basic neonatal resuscitation.^{1,2} The International Liaison Committee on Resuscitation (ILCOR) publishes a consensus on newborn resuscitation science every 5 years and currently recommends monitoring of oxygen saturation (SpO₂), heart rate (HR; monitored by electrocardiography), and skin temperature (T_{skin}) during neonatal resuscitation.³ Therefore, in the delivery room, the use of expensive and large base monitoring units attached to a power supply is usually necessary. To obtain the signals, wired skin sensors and electrodes are placed on the patient. Altogether, these are barriers for adoption of the ILCOR recommendations due to the lack of portability and the training required for their use in environments with low resources and high number of deliveries.⁹ Indeed, many delivery centers in low and middle income countries (LMIC) either do not monitor or use a variety of different systems whose accuracy and safety is unknown (**Figure 1**). The Argentine Pediatrics Society, after evaluating the causes of neonatal deaths of hospitalized newborns, reported that, at the time of death, many newborns were not adequately monitored, concluding that lack of adequate neonatal vital sign monitoring may contribute to an increase in preventable newborn unexpected catastrophic events leading to death.¹⁰ Furthermore, the necessary equipment is usually in the same room of the mother, demanding close communication within teams and with the family. However, delivery room (DR) technologies should facilitate, rather than impede, family integration and early bonding. Additionally, infants are born with wet skin and a transitioning cardiorespiratory system, but existing monitoring solutions were not primarily designed for resuscitation and may also have a significant delay (up to 1 minute) before displaying data, which can affect critical clinical decisions. As knowledge about the process involving the transition from fetal to neonatal life increases, it is expected that more technologies will evolve for use in the DR. These technologies should be developed for use where the greatest burden of morbidity and mortality exists (LMIC) to have the largest impact in neonatal health care.^{1,2}

[figure not shown]

Figure 1. Monitoring in a maternity hospital located in the northeastern region of Brazil. **A** – Delivery room: note lack of monitoring at the resuscitation unit where there are no devices to capture ECG and SpO₂. **B to F** Five different monitoring devices used in the same NICU. All placed on the top of the incubators and using different technologies.

In the majority of infants that do not require resuscitation after delivery, Kangaroo Mother Care (KMC) is a common practice associated with several advantages for maternal and neonatal health and is supported by the World Health Organization (WHO). Skin-to-skin care shortly after birth improves temperature stabilization and facilitates initial breastfeeding. Thus, KMC should start in the obstetrical center.⁴⁻⁶ However, unsupervised skin-to-skin care may contribute to bedsharing, a practice specifically discouraged by the American Academy of Pediatrics as unsupervised post-partum KMC has been identified as a major risk factor for sudden unexpected postnatal collapse (SUPC), which mostly occurs during the **first 2 hours of age**.⁷ SUPC is an apnea or cardiorespiratory failure occurring in an otherwise-healthy near term or term newborn during the initial skin-to-skin contact, with prone positioning, or with the first attempt to breastfeed. The incidence has been estimated to be between 2.6-133 cases per 100.000 newborns.^{8,9,11} Despite educational efforts, falling asleep while breastfeeding or holding a newborn during skin-to-skin care is a hazard after sleep deprivation and/or the use of narcotic analgesics associated with labor & delivery. In over 50% of cases, SUPC occurs following accidental suffocation, and frequently goes unrecognised by parents. For this reason, some health care authorities have recommended development and implementation of safety guidelines in hospitals. Nonetheless, as many as 60% of SUPC cases still occur in centers that have adopted these guidelines.

1.2 Study Rationale

Delivery room and hospital care requires new and advanced technology that can quickly capture and monitor vital signs from birth up to discharge home. Such technology must have several characteristics. It should be small, non-invasive, not require installation of expensive and sophisticated equipment, be easily accessible by health care professionals, affordable, portable, and non-intrusive to promote early and safe skin-to-skin contact between mothers and their newborns. In the hospital setting, a balance is needed between encouraging and supporting a mother while avoiding practices that inadvertently increase the risks to the infant. A number of emerging technologies have been investigated for neonatal vital sign monitoring including camera-based (visible light and infrared thermography), RADAR, Ballistocardiograph, and capacitive ECG.¹²⁻²² Studies were mostly done in the Neonatal Intensive Care Unit (NICU). Camera-based monitoring was examined for HR measurements, but the equipment is expensive, needs to be placed perpendicularly and at a specific distance in front of the infant's face. Additionally, a large band light source is required to uniformly illuminate the selected area on infants in a supine position, allowing direct camera view.¹²⁻¹⁴ Camera thermal recordings were investigated for measurements of RR in a control environment with good accuracy. However, thermal imaging is very expensive, sensitive to motion artifacts, and requires wires and cables to connect all the equipment around the infant.¹⁵⁻¹⁷ Ballistocardiography provides unobtrusive measurements of HR and Respiratory Rate (RR) and could be useful for monitoring biological signals without physical limitations.¹⁸ However, signal processing is difficult due to noise, inherent physiological variability, and artifacts. Only one small study was done in neonates and no signal processing improvement was tested in this population. Moreover, it is not usable during KMC since Ballistocardiograph signal was acquired using bed-based load cells. Capacitive sensing of electrocardiographic uses ECG leads embedded on clothes or mattress but requires wires.^{19,20} In one study, lead electrodes were connected to a device using shielded wires 2.0m long.²⁰

Fortunately, the past decade has seen tremendous breakthroughs in the field of biosensor technology leading to a surge in wireless skin sensors and devices.²³⁻²⁶ These bio-integrated sensors have been developed and investigated in neonates, providing the prospect of enhancing monitoring capabilities, reducing iatrogenic injuries, and promoting family-centered care, thereby stirring expectations for the use of this technology in the delivery room. A new advanced wireless system was specifically developed for neonates and has the potential to be used immediately after birth as a non-invasive and non-intrusive

system (ANNEArc™ and RAD7 limb sensor SIBEL HEALTH INC, ILLINOIS, USA - Masimo). However, this new technology requires testing in delivery care facilities on a large scale and in different countries, to clearly establish its feasibility, accuracy, and safety. This large prospective study – **the AWARD study** - will use the ANNEArc and RAD7 limb sensor in low-risk infants immediately after vaginal and c-section delivery for the first 2h of age while under parents' care in the obstetrical center.

Healthcare technology continues to advance at remarkable rates, but its assessment lags significantly.²⁷ The cost of healthcare technology assessment is less than 0.3% of the total amount spent on healthcare, as reported by the Institute of Medicine.²⁸ Recently, the Neonatal Resuscitation Section Writing Group of the European Society for Paediatric Research (ESPR) published a review on “the newborn delivery room of tomorrow: emerging and future technologies”.⁹ An online survey reported that funding for development of DR technologies has been poor. Future monitoring of vital signs by using wireless technology was ranked as important or highly important by almost 80% of the respondents. Nevertheless, few studies have properly investigated feasibility, safety, and accuracy of new devices. For healthy near-term and term infants, it is also extremely important to assess if this new technology could help safely promote KMC after delivery, without supervision. This would fulfill a need for enhanced safety measures to prevent catastrophic events such as SUPC, and potentially save thousands of lives per year. Although SUPC is a rare cause of mortality, it deserves attention because it may be largely preventable.

This work may promote and improve monitoring of all neonates immediately after delivery and during unsupervised KMC in the obstetrical center while under parents' care by using a non-invasive, non-intrusive, portable, and low-cost wireless technology. It may also lead to testing of this technology during neonatal resuscitation and prevent deaths related to SUPC in hospitals. Due to the low-cost of implementation and training, this technology could be quickly adopted for widespread use in LMIC.

1.3 Preliminary Data

Over the last 2.5 years our group has conducted a series of studies on the use of wireless technology in preterm and term neonates under the SMART Hospital Project. We started the project by conducting a systematic review of all published literature on wearable devices in neonates²⁹ and children, followed by a Scoping Review on the use of wireless technology in hospitalized children.³⁰ After these reviews, we selected a wireless sensor developed by the Laboratory of [name] at Northwestern University optimized & commercialized by Sibel Health, Inc. for evaluation. The safety and accuracy of these sensors were previously investigated in a few neonates for short periods of time, however we felt that healthcare technology assessment in a variety of NICU infants for longer recording periods was necessary.^{23,24} To this end, we established a Research & Development collaboration with Sibel Health, Inc. and conducted a *phase 1a* study in our NICU at the Montreal Children's Hospital to evaluate ANNE One® sensors. A hardware/software system called BioDASH was developed for this study by Ikenesia Inc. (<https://www.ikenesia.com/>; Montreal, Quebec, Canada) to allow simultaneous recording of vital signs from a wired (standard of care) and a wireless system in 25 infants, 8h per day during 4 consecutive days.³¹ In order to ensure the research team performing was adequately prepared to perform the Phase 1a study, they participated in training on how to handle, place and remove the wireless sensors prior to the start of data collection. There were no reports or feedback by the research team of any difficulty related placement or removal of the wireless skin sensors. Heart rate, respiratory rate, oxygen saturation, and skin temperature were recorded. Full analysis of the data is underway, with some results presented and published. HR analysis of the first 10 patients enrolled was presented at the Pediatric Academic Society (PAS) meeting in Washington, DC USA (April 27-May 1 2023) showing an excellent agreement between the two systems for HR values.³² (**Figure 2**).

[figure not shown]

Figure 2. Regression analysis of ANNE One® and Philips HR signals for HR.

This accuracy analysis was recently completed for all 25 infants and confirmed the strong agreement between HR recorded by the wired and wireless systems with ANNE® One, showing a strong potential for wireless monitoring in the NICU³³ (**Figure 3**).

Ongoing work includes the analysis of RR, SpO₂ and T_{skin} signals to evaluate the overall feasibility, reliability, and accuracy of ANNE® One sensors.

[figure not shown]

Figure 3. Cumulative histograms of HR recorded with a wired (blue) and a wireless system (red) for a typical subject

Additionally, we developed methods to synchronize and align all signals acquired from the wired and wireless monitors to allow sample-to-sample comparison.³³ (**Figure 4**).

[figure not shown]

Figure 4. The sample signals following pre-processing, where: (A) the short gap was filled, (B) aligned features share a common time due to resampling, (C) the initial delay was removed, and (D) the signals remain aligned 6 hours later due to drift correction.

More recently, the feasibility of this wireless system was evaluated by correlating periods of missing data in HR with automatically generated alert signals and manually recorded annotations. (**Figure 5**). Gaps in the wireless HR signals were most often linked to Bluetooth disconnections and KMC. Current work is examining the roles of: (1) movement artifact, (2) signal to-noise ratio, as a means to understand problems and improve the feasibility of using a wireless system in the NICU. ³⁴

[figure not shown]

Figure 5. Group results from HR gap classification pertaining to: (A) the correlation of gaps in the wireless system with alert flags, and (B) the correlation of gaps in both the wireless and wired systems with the seven-most prominent comment codes. HR sample coverage = 86%.

Based on these results and on interviews conducted with parents and NICU nurses, Sibel made important modifications to the ANNE One® chest sensor, including its size, shape (configuration), position of the antenna, and type of skin adhesive. The new sensor called ANNE Arc® is now available, has been approved by Health Canada for research (ITA), and will be used in this Study along with the RAD7 Limb Sensor (**Figure 6, Figure 7**). Moreover, a large international survey on the use of wired and wireless technology in the NICU was circulated to HCPs all over the world. Almost 1000 HCPs have replied, and analysis is underway. Finally, in collaboration with researchers at Northwestern University, a wireless acoustic device for

monitoring airflow, breathing efforts and bowel sounds was developed and tested. Results were presented at the PAS meeting in May 2023, and the manuscript was accepted for publication in *Nature Medicine*.³⁵

[figure not shown]

Figure 6. Amplified image of the ANNE Arc sensor. The sensor has 2 ECG leads (HR and RR), a temperature sensor (skin temperature), and an accelerometer (body movements).

[figure not shown]

Figure 7. Overview of the ANNE Arc system showing all components, including the adhesives, correct placement on the chest, and the wireless charger.

2 Study Hypothesis, Aims and Purpose

2.1 Hypothesis

Is a new advanced and non-intrusive wireless skin sensor system feasible, safe, and accurate for monitoring infants immediately after birth and for the first 2h of age, while in the obstetrical center and under unsupervised parents' care in high, lower, and middle income countries

2.2 Aims

Healthcare technology assessment is the multidisciplinary evaluation of medical technologies with regard to **feasibility, safety, efficacy**, indications for use, cost, and cost-effectiveness. A complete assessment should explore the scientific, ethical, economic, and social reasons for adopting a technology and it may influence the quality of service and distribution of resources.

In this multicenter study, we aim to assess the first 3 important criteria.

Aim 1 – To determine the **feasibility** of using a wireless system immediately after delivery and for the first 2h of age, while in the obstetrical center under unsupervised parents' care. The following outcomes will be measured for both wired and wireless systems:

- a. Percentage of time for which HR, RR, SpO₂ and T_{skin} data are displayed.
- b. Occurrence of gaps in signal detection/recordings (% and length).
- c. Causes of the gaps in signal detection/recordings.
- d. Descriptive analysis of user surveys and their satisfaction with the wireless system.

Aim 2 - To investigate the **safety** of using this wireless system immediately after delivery and for the first 2h of age. The following outcomes will be measured for both wired and wireless systems:

- a. Skin score to be determined by a blinded dermatologist using de-identified pictures of the skin after removal of the sensors of each system.
- b. Pain scale to assess any discomfort or pain during the removal of the sensors.
- c. Clinically significant events detected by the wired system (HR < 100 bpm or SpO₂ < 80%) but missed by the wireless system.

Aim 3 – To assess the **accuracy** of this wireless system in measuring HR, RR, SpO₂ and T_{skin} signals compared with the “standard of care” wired system. The following outcomes will be computed:

- a. Correlation coefficient
- b. Slope
- c. Variance accounted for
- d. Bias

Further subgroup analyses will be conducted to assess for systematic differences in feasibility, safety, and accuracy of the wireless system between the following:

- High vs. Low and Middle income countries
- Female vs. Male subjects
- Term vs. Preterm (born < 37 weeks gestational age) infants
- C-section vs. Vaginal delivery

- Skin pigmentation

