- Skin Pigment: Previous research has highlighted the challenges of some pulse oximeters in providing accurate readings for skin with darker pigmentation and as a result has emphasized the need to investigate the performance of pulse oximeters for different skin tones^{38,39}. The infant's skin color will be recorded using the adapted Munsell System Soil Color Chart (2009 Revision, Munsell Color, Grand Rapids, Michigan), Hue7.5YR to investigate impact of skin pigmentation on pulse oximetry accuracy. This scale has previously been used in research on neonates⁴⁰.
- *Pain Assessment*: As well, neonatal pain will be assessed throughout the sensor removal process. The pain scale (NIPS) will be completed by the study team member at the time of sensor removal and entered into REDCAP.
 - Neonatal Infant Pain Scale (NIPS)³⁶ : At the time of device removal, the researcher will complete the NIPS to ensure removal of adhesive does not cause significant discomfort to the patient. The scale consists of 6 items. Scores range from 0 to 7, with scores greater than 3 indicating presence of pain. This scale has been widely validated for the assessment of acute pain in neonates. This scale will be included in the Data Collection Form.
- *Surveys*: In order to assess feasibility on the use of wireless sensors to monitor babies after birth, a survey will be conducted to get the opinions of parents and Health Care Professionals involved in the care of the baby and mother. The survey will be presented in hard copy form as well as through REDCAP.
 - Parent Survey: Parents of the participating infant will be asked to complete a short survey to after the sensors of both systems are removed. The survey will be coded with the study code assigned to the participating infant, no personal health information or personal information will be asked of the parent for the completion of the survey. (See Appendix 2).
 - Health Care Professional Survey: HCPs involved in the care of the infant and mother after birth will be asked to complete a short survey after the sensors of both systems are removed in order to assess how the HCPs felt about the wireless skin sensors as compared to their experience of the standard of care wired monitoring system. (See Appendix 2).

REDCAP

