Appendix
(photos)

APPENDIX 2

PARENT SURVEY

Subject ID:

() Mother () Father () Other: _____

Section 1: Your experience with the Wired Monitoring

1. How satisfied are you with the system?
 - a. Very dissatisfied
 - b. Dissatisfied
 - c. Neutral
 - d. Satisfied
 - e. Very satisfied

1. What are your concerns? (Mark all that apply - multiple choices are permitted)
 - a. Problems with the stickers on my baby's skin
 - b. Too many stickers on my baby's skin
 - c. Too many wires around my baby
 - d. Difficult to touch my baby because of the stickers and wires
 - e. The stickers, wires and monitors are concerning
 - f. No concerns
 - g. Other (please specify): _____

1. The monitors and wires interfere with my ability to do skin-to-skin (Kangaroo) care:
 - a. Strongly disagree
 - b. Disagree
 - c. Neutral
 - d. Agree
 - e. Strongly agree

1. What kind of problems have you seen with the use of the wired monitoring system? (Mark all that apply - multiple choices allowed)
 - a. Skin lesions associated with chest adhesives
 - b. Skin lesions associated with the limb probe
 - c. Pressure sore associated with chest adhesives
 - d. Pressure associated with the limb probe
 - e. Fear of handling my baby because of the multiple wires and cables
 - f. Wires tangled around the baby chest or limbs
 - g. Wires soiled – requiring replacement or cleaning
 - h. Cables soiled – requiring replacement or cleaning
 - i. Installation time
 - j. Wires disconnected
 - k. Cables disconnected

I. Other:

1. The adhesives, sensors, wires, and monitors, can prevent me from bonding with my baby:
 - a. Strongly disagree
 - b. Disagree
 - c. Neutral
 - d. Agree
 - e. Strongly agree

Section 2: Your experience with the Wireless Monitoring

1. What is your opinion about the use of a new wireless technology to monitor your baby's vital signs?

Chest sensor

- a. Strongly oppose
- b. Somewhat oppose
- c. Neutral
- d. Somewhat favor
- e. Somewhat favor
- f. Strongly favor

Limb sensor

- a. Strongly oppose
- b. Somewhat oppose
- a. Neutral
- c. Somewhat favor
- d. Somewhat favor
- e. Strongly favor

1. I am worried about the safety and the accuracy of the new wireless technology.

Chest sensor

- a. Strongly disagree
- b. Disagree
- c. Neutral
- d. Agree
- e. Strongly agree

Limb sensor

- a. Strongly disagree

- b. Disagree
- a. Neutral
- c. Agree
- d. Strongly agree

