1. What are your main concerns with the implementation of a new wireless technology in the Delivery Room? (Mark any that apply - multiple choices permitted)

Chest Sensor

- a. Accuracy (good and reliable data)
- b. Challenges using sensors
- c. Safety of stickers used to apply sensors
- d. Size of the sensors
- e. Weight of the sensor
- f. Battery life of wireless sensors
- g. No concerns
- h. Other (please specify):

Limb Sensor

- a. Accuracy (good and reliable data)
- b. Challenges using sensors
- c. Safety of stickers used to apply sensors
- d. Size of the sensors
- e. Weight of the sensor
- f. Battery life of wireless sensors
- g. No concerns
- h. Other (please specify):

1. What do you think might be the impact of a wireless system on bonding between parents and their babies?

- a. Strongly negative
- b. Negative
- c. Neutral
- d. Positive
- e. Strongly positive

1. What do you think might be the impact of a wireless system on your baby's hospital experience? (Mark any that apply - multiple choices permitted)

- a. Easier Kangaroo care (KC) initiation
- b. Increase the amount of time on KC
- c. Reduce discomfort

- d. Decrease pain
- e. Better sleep
- f. Newborn safety
- g. None
- h. Other (please specify):

1. Any additional comment (s):

DO NOT COPY

HEALTH CARE PROFESSIONAL'S SURVEY

Subject ID:

() Neonatologist () Neonatal Fellow () Pediatric Resident

() Registered Nurse () Neonatal Nurse Practitioner

() Respiratory Therapist

() Other: _____

Years of experience: () < 2 years () 2-5 years () 6-10 years () > 10 years

Section 1: Current State of Monitoring with Wires and Cables

1. How satisfied are you with the use of monitoring system with wires and cables immediately after birth and up to 2h of age in the DR?

- a. Very dissatisfied
- b. Dissatisfied
- c. Neutral
- d. Satisfied
- e. Very satisfied

2. What are your main concerns with the monitoring system with wires and cables? (Mark any that apply - multiple choices permitted)

- a. Inaccurate readings
- b. False alarms
- c. Issues associated with adhesion of the sensors (heat generation or pressure and skin irritation)
- d. Too many sensors applied to the skin
- e. Too many wires around the baby
- f. Difficult to handle the baby because of the multiple wires and cables
- g. The sensors, wires and cables are intimidating to the parents
- h. I do not have concerns
- i. Others (please specify): _____

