3. What are the main benefits of using a wired and cable monitoring system immediately after birth and up to 2h of age in the DR? (Mark any that apply - multiple choices allowed)

- a. Easy to use
- b. Various functions in this system were well integrated
- c. Quickly to learn how to use
- d. Fast speed of data display
- e. There are no benefits

f. Others (please specify):

4. How confident are you with the use of monitoring system with wires and cables immediately after birth and up to 2h of age in the DR?

- f. Not confident
- g. Somewhat not confident
- h. Neutral
- i. Somewhat Confident
- j. Confident

5. What kind of problems did you see by using the current standard monitoring system in healthy babies immediately after birth and up to 2h of age in the DR? (Mark any that apply - multiple choices permitted)

- a. Skin lesions associated with ECG adhesives
- b. Skin lesions associated with the oxygen saturation sensor
- c. Pressure sores associated with ECG adhesives
- d. Pressure sores associated with the oximeter sensors
- e. Parents afraid to handle their baby because of the multiple wires and cables
- f. Wires tangled around the baby's chest or limbs
- g. Wires soiled – requiring replacement or cleaning
- h. Cables soiled – requiring replacement or cleaning
- i. Wires disconnected
- j. Cables disconnected
- k. Other:

6. List any other perceived benefits and disadvantages of the system:

Section 2: Wireless Monitoring System in the Delivery Room

7. What is your attitude towards the use of this new wireless chest sensor technology in the Delivery Room?
 - a. Very skeptical
 - b. Skeptical
 - c. Neutral
 - d. Optimistic
 - e. Very optimistic
8. What is your attitude towards the use of this new wireless limb sensor technology in the Delivery Room?
 - a. Very skeptical
 - b. Skeptical
 - c. Neutral
 - d. Optimistic
 - e. Very optimistic
9. What is your level of concern regarding the safety and accuracy of using this new wireless chest sensor technology, immediately after birth and up to 2h of age in the DR?
 - a. Very concerned
 - b. Somewhat concerned
 - c. Neutral
 - d. Somewhat concerned
 - e. Not concerned at all
10. What is your level of concern regarding the safety and accuracy of using this new wireless limb sensor technology, immediately after birth and up to 2h of age in the DR?
 - a. Very concerned
 - b. Somewhat concerned
 - c. Neutral
 - d. Somewhat concerned
 - e. Not concerned at all

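### Appendix 2 asks about satisfaction and problems seen only for the wired system, so the satisfaction part of Aim 1d can be addressed only indirectly; four of nine wireless rating scales also carry a duplicated label

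*Combined protocol and SAP*

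**What the plan says.** Section 2.2 lists four feasibility outcomes under Aim 1, introduced by "The following outcomes will be measured for both wired and wireless systems". The last, Aim 1d, is the "Descriptive analysis of user surveys and their satisfaction with the wireless system".

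Section 3.3.4 gives the staff survey a comparative purpose: to "assess how the HCPs felt about the wireless skin sensors as compared to their experience of the standard of care wired monitoring system". It also fixes the timing: "Parents of the participating infant will be asked to complete a short survey to after the sensors of both systems are removed". The staff survey is given at the same point, so every respondent answers after both systems have been used.

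In Appendix 2, the parent satisfaction question, "How satisfied are you with the system", stands in Section 1, which is headed as the experience with wired monitoring. Staff item 1 reads "How satisfied are you with the use of monitoring system with wires and cables immediately after birth". Staff item 5 reads "What kind of problems did you see by using the current standard monitoring system in healthy babies". On the wireless side, staff item 9 (repeated for the limb sensor as item 10) asks "What is your level of concern regarding the safety and accuracy of using this new wireless chest sensor technology".

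Section 5.1 states that the lead site will carry out interim safety evaluations after 200 and 400 patients, and names staff survey responses among the data reviewed.

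**The concern.** The outcome named in Aim 1d is satisfaction with the wireless system, yet the satisfaction questions are about the other system. A satisfaction rating that was not asked for at the time cannot be recovered by later analysis. If the forms are used as printed, the report will hold a wired satisfaction rating with no wireless counterpart, and lists of wired problems seen with no wireless list beside them.

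The duplicated labels are a separate defect. If two options on an ordered scale read the same, an answer stored by its label cannot be placed. In staff items 9 and 10 the repeated label lies on both sides of Neutral. These are the only graded items in the staff survey on the safety and accuracy of the wireless sensors, and that survey is an input to the interim safety reviews.

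**Working it through.** The plan gives no figure to reproduce here, and no sample-size or power calculation enters. The check is an item-by-item comparison of the wired and wireless sections of both surveys in Appendix 2, followed by a count of the wireless rating scales.

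**Step 1. Items by system** (number of response options in brackets)

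| Topic | Wired, parents | Wired, staff | Wireless, parents | Wireless, staff |
|---|---|---|---|---|
| Satisfaction rating | 1 | 1 (item 1) | 0 | 0 |
| Problems-seen checklist | 1 (12) | 1 (item 5; 11) | 0 | 0 |
| Rated interference with skin-to-skin care | 1 | not asked | 0 | not asked |
| Confidence rating | not asked | 1 (item 4) | not asked | 0 |
| List of benefits of use | not asked | 1 (item 3; 6) | not asked | 0 |
| Concerns checklist | 1 (7) | 1 (item 2; 9) | 2 (8 chest, 8 limb) | 2 (items 11 and 12; 8 chest, 9 limb) |
| Bonding rating | 1, agreement scale | not asked | 1, expected-impact scale | not asked |
| Possible-impact checklist | 0 | 0 | 1 (8) | 1 (item 13; 8) |

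Satisfaction items: wired 1 + 1 = 2, wireless 0 + 0 = 0. Problems-seen items: wired 1 + 1 = 2, wireless 0 + 0 = 0.

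Concerns and bonding are asked for both systems. The bonding items do not match: the wired one asks for agreement that the equipment can get in the way, while the wireless one asks what the effect might be. Skin-to-skin care appears on the wireless side only as options in the possible-impact checklists, not as a rated item.

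**Step 2. Wireless rating scales (single choice)**

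| Scale | Number | Labels |
|---|---|---|
| Parent opinion, chest and limb | 2 | *Somewhat favor* printed twice in each |
| Parent worry, chest and limb | 2 | five distinct, ordered |
| Parent bonding | 1 | five distinct, ordered |
| Staff attitude, items 7 and 8 | 2 | five distinct, ordered |
| Staff concern, items 9 and 10 | 2 | *Somewhat concerned* is both option b and option d, either side of Neutral |

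Total 2 + 2 + 1 + 2 + 2 = 9. With a duplicated label: 2 + 2 = 4 of 9. Sound: 5 of 9.

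**Step 3. What each duplication does**

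- Parent opinion: the six printed options contain two identical neighbours. Merging them leaves 6 − 1 = 5 options: two unfavourable, one neutral, two favourable. Answers already given remain usable.
- Staff items 9 and 10: with options a to e scored 1 to 5, an answer stored as *Somewhat concerned* could be 2 or 4, an ambiguity of 4 − 2 = 2 points across the neutral value. If the option letter was stored, the position is known, but a respondent who chose d after reading its label may have meant b.

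Each duplicate has its own option letter and recurs in both the chest and limb versions, so an error in reading the PDF is unlikely. The repeated question numbers and irregular limb-scale lettering may be such errors, and nothing here rests on them.

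**The case against.** The best defence is that Aim 1d asks for a descriptive analysis of the surveys, and that analysis can be done. Parents give opinion, worry, concerns, expected effects and free comments on the wireless system; staff give attitude, level of concern, concerns, expected effects and free comments. This stands. A reader might infer that Aim 1d cannot be answered at all, but the documents do not support that: what is missing is the direct rating and its wired comparison.

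A reader might also infer that the wireless scales are faulty in general. Five of the nine are sound.

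The most tempting stronger reading is that the forms favour the wireless system by design, since respondents are prompted for wired problems seen and for possible wireless benefits. The net direction is not established. Wireless concerns are prompted with 8 or 9 options per sensor, against 7 and 9 for the whole wired system. Staff item 3 prompts for wired benefits. In staff items 9 and 10, three of five options read as concerned, which would count against the wireless system. Wireless problems are also recorded outside the surveys: Appendix 1 logs skin irritation, erosion and bleeding for both systems, along with sensor disconnections, readjustments and limb sensors falling off, and Aims 1b and 1c cover signal gaps and their causes. What is absent is the users' own report of wireless problems.

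Finally, Aim 1d is the last of four feasibility outcomes, is descriptive, and has no sample-size calculation attached. That limits the severity. It does not remove the mismatch between a named outcome and the form meant to measure it.

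**Conclusion.** The point holds within these limits. Neither survey has a satisfaction item or a problems-seen item for the wireless system (wired: one of each per survey; wireless: none). Rated skin-to-skin interference (parents) and confidence and benefits (staff) are likewise asked only for the wired system. The satisfaction part of Aim 1d can therefore be reached only indirectly, and the two-system measurement in section 2.2 and the staff comparison in section 3.3.4 cannot be made like for like on satisfaction or problems seen.

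Four of nine wireless rating scales have a duplicated label. The two parent scales can be repaired by merging. The two staff scales are the more serious because of their place in the interim safety reviews, although skin events are recorded separately for both systems, so safety monitoring does not depend on the survey alone.

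Severity is moderate. The conclusion assumes that the forms printed in Appendix 2 are those used at the sites and entered in REDCap.

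**What to change.** In Appendix 2, before use or for all remaining infants:

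1. Repeat the wired satisfaction and problems-seen items for the wireless system in both surveys, with the same wording and scale. Problem options that make sense only for wires or cables need a sensor counterpart; the skin-lesion and pressure options should stay matched so that they can be compared.
2. Repeat the parent skin-to-skin interference item and the staff confidence item for the wireless system in the same way.
3. Remove the duplicate *Somewhat favor* from the parent opinion item, chest and limb.
4. Correct option d in staff items 9 and 10 so that the five labels are distinct and ordered.

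For forms already completed, merge the two *Somewhat favor* options. For staff items 9 and 10, check whether the option letter was stored, and report answers from the old form separately from those on the corrected scale. The interim safety reviews should do the same.

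Aim 1d can stay descriptive; it need not be redefined as a within-respondent difference. With matched items in place, the wired and wireless ratings can simply be shown side by side.

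Cost: survey and REDCap edits, retranslation, an ethics amendment, and three more questions per respondent (parents: satisfaction, problems seen, skin-to-skin interference; staff: satisfaction, problems seen, confidence).
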